- 10. ALT or AST should be ≤ULN at Screening or Check-in (for these parameters, a subject with out-of-range values may have the tests repeated once and the subject may be enrolled if the repeated values are ≤ULN or if the repeated values above ULN are deemed not clinically significant by the Investigator [eg, 1.5 x ULN]).
- 11. Positive hepatitis B or hepatitis C panel and/or positive human immunodeficiency virus test at Screening. Subjects whose results are compatible with prior immunity (vaccination or prior infection) may be included.
- 12. Use of any over-the-counter or prescription medications within 30 days or 5 half-lives (whichever is longer) before enrollment, unless deemed acceptable by the Investigator (or designee) and in consultation with the Sponsor.
 - a. Acetaminophen [paracetamol] (up to 2 g per day) for analgesia will be allowed.

18 May 2022 Page 22 of 69

- 13. All herbal medicines (eg, St. John's wort), vitamins, and supplements consumed by the subject within the 30 days prior to enrollment, unless deemed acceptable by the Investigator (or designee) and in consultation with the Sponsor.
- 14. Consumption of foods and beverages containing poppy seeds, grapefruit, or Seville oranges within 7 days prior to Check-in.
- 15. History of alcoholism or drug/chemical abuse within 1 year prior to Check-in.
- 16. Alcohol consumption from 48 hours prior to Check-in.
- 17. Regular alcohol consumption of > 14 units per week for males and > 7 units per week for females. One unit of alcohol equals 12 oz (360 mL) beer, 1½ oz (45 mL) liquor, or 5 oz (150 mL) wine.
- 18. Use of tobacco- or nicotine-containing products within 6 months prior to Check-in.
- 19. Positive test for illicit drugs, cotinine (tobacco or nicotine use) at Screening or Check-in and/or alcohol use at Check-in only.
- 20. Consumption of caffeine-containing foods and beverages within 48 hours prior to Check-in.
- 21. Female subjects with a positive pregnancy test at Screening or Check-in.
- 22. Female subjects lactating/breastfeeding or who plan to breastfeed during the study through 7 days after the EOS.
- 23. Unwilling to adhere to contraceptive requirements through 7 days after the EOS (see).
- 24. Unwilling to abstain from sperm donation through 7 days after the EOS (see).
- 25. Male subjects with a female partner of childbearing potential and not willing to inform his partner of his participation in this clinical study.

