Appendix 2: Clinical Laboratory Evaluations

Clinical chemistry:	Hematology:	Urinalysis:			
Alanine aminotransferase Albumin Alkaline phosphatase Aspartate aminotransferase Blood urea nitrogen Calcium Chloride Cholesterol Creatinine Direct bilirubina Gamma-glutamyl transferase Glucose Indirect bilirubina Inorganic phosphate Magnesium Potassium Sodium Total bilirubina Total CO2 (measured as bicarbonate) Total creatine kinase Total protein Uric acid	Hematocrit Hemoglobin Mean cell hemoglobin Mean cell hemoglobin concentration Mean cell volume Platelet count Red blood cell (RBC) count RBC distribution width White blood cell (WBC) count WBC differential: Basophils Eosinophils Lymphocytes Monocytes Neutrophils	Bilirubin Blood Color and appearance Glucose Ketones Leukocyte esterase Nitrite pH Protein Specific gravity Urobilinogen Microscopic examination (if protein, leukocyte esterase, nitrite, or blood is positive)			
Serology ^b :	Drug screen ^c :	Hormone panel - females only:			
Anti-hepatitis B surface antibody Anti-hepatitis B core antibody Hepatitis B surface antigen Hepatitis C antibody Human immunodeficiency virus (HIV-1 and HIV-2) antibodies and p24 antigen	Including but not limited to: Amphetamines/methamphetamin es Barbiturates Benzodiazepines Cocaine (metabolite) Cotinine test Methadone	Follicle-stimulating hormone ^b (postmenopausal females only) Serum pregnancy test (human chorionic gonadotropin) ^d Urine pregnancy test ^d			
	Phencyclidine Opiates Tetrahydrocannabinol/ cannabinoids Tricyclic antidepressants Alcohol urine or alcohol breath test (Check-in only)	Other tests: International normalized ratio (INR) ^e Estimated glomerular filtration rate (eGFR) ^{e,f} Thyroid-stimulating hormone ^g			

^a Direct and indirect bilirubin will be analyzed if total bilirubin is elevated.

18 May 2022 Page 50 of 69

^b Only analyzed at Screening.

^c Only analyzed at Screening and Check-in.

^d Performed at Screening, Check-in, and at the end of study or if a subject is withdrawn early from the study. Performed in serum at Screening and in urine at all other times for all females. A positive urine pregnancy test will be confirmed with a serum pregnancy test.

18 May 2022 Page 51 of 69

^e International normalized ratio will be tested if hepatotoxicity is suspected, per guidelines presented in Appendix 7. ^f Calculated by the Modification of Diet in Renal Disease equation.

g. Only analyzed at Screening, Check-in, and at end of study.

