Appendix 7: Hepatotoxicity Stopping Rules: Suggested Actions and Follow-up Assessments

Subjects with abnormal hepatic laboratory values (ie, alkaline phosphatase [ALP], aspartate aminotransferase [AST], alanine aminotransferase [ALT], total bilirubin [TBL]) and/or international normalized ratio (INR) and/or signs/symptoms of hepatitis (as described below) may meet the criteria for withholding or permanent discontinuation of Amgen investigational product or other protocol-required therapies, as specified in the Guidance for Industry Drug-Induced Liver Injury: Premarketing Clinical Evaluation, July 2009.

Criteria for Withholding and/or Permanent Discontinuation of Amgen Investigational Product and Other Protocol-required Therapies Due to Potential Hepatotoxicity

The following stopping and/or withholding rules apply to subjects for whom another cause of their changes in liver biomarkers (TBL, INR, and transaminases) has not been identified.

Important alternative causes for elevated AST/ALT and/or TBL values include, but are not limited to:

- Hepatobiliary tract disease
- Viral hepatitis (eg, hepatitis A/B/C/D/E, Epstein-Barr Virus, cytomegalovirus, herpes simplex virus, varicella, toxoplasmosis, and parvovirus)
- Right-sided heart failure, hypotension, or any cause of hypoxia to the liver causing ischemia
- Exposure to hepatotoxic agents/drugs or hepatotoxins, including herbal and dietary supplements, plants, and mushrooms
- Heritable disorders causing impaired glucuronidation (eg, Gilbert's syndrome, Crigler-Najjar syndrome) and drugs that inhibit bilirubin glucuronidation (eg, indinavir, atazanavir)
- Alpha-one antitrypsin deficiency
- Alcoholic hepatitis
- Autoimmune hepatitis
- Wilson's disease and hemochromatosis
- Nonalcoholic fatty liver disease including steatohepatitis
- Non-hepatic causes (eg, rhabdomylosis, hemolysis).

If investigational product(s) is/are withheld, the subject is to be followed for possible drug-induced liver injury (DILI) according to recommendations in the last section of this appendix.

18 May 2022 Page 63 of 69

Rechallenge may be considered if an alternative cause for impaired liver tests (ALT, AST, ALP) and/or elevated TBL is discovered and the laboratory abnormalities resolve to normal or baseline (see next section in this appendix).

Table 2: Conditions for Withholding and/or Permanent Discontinuation of Amgen Investigational Product and Other Protocol-required Therapies Due to Potential Hepatotoxicity

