Analyte	Temporary Withholding	Permanent Discontinuation
TBL	>3x ULN at any time	>2x ULN
INR		>1.5x ULN (for subjects
	OR	not on anticoagulation therapy)
		AND
AST/ALT	>8x ULN at any time	In the presence of no important alternative
	>5x ULN but $<8x$ ULN for ≥ 2 weeks	causes for elevated AST/ALT and/or TBL
	>5x ULN but <8x ULN and unable to adhere to enhanced monitoring schedule	values
		>3x ULN (when baseline
	>3x ULN with clinical signs or symptoms that are consistent with hepatitis (such as right upper quadrant pain/tenderness, fever, nausea, vomiting, and jaundice)	was < ULN)
	OR	
ALP	>8x ULN at any time	

Abbreviations: ALP = alkaline phosphatase; ALT = alanine aminotransferase; AST = aspartate aminotransferase; INR = international normalized ratio; TBL = total bilirubin; ULN = upper limit of normal.

Criteria for Rechallenge of Amgen Investigational Product and Other Protocol-required Therapies After Potential Hepatotoxicity

The decision to rechallenge the subject is to be discussed and agreed upon unanimously by the subject, Investigator, and Amgen.

If signs or symptoms recur with rechallenge, then sotorasib is to be permanently discontinued.

18 May 2022 Page 64 of 69

Subjects who clearly meet the criteria for permanent discontinuation (as described in Table 2) are never to be rechallenged.

Drug-induced Liver Injury Reporting and Additional Assessments

Reporting

To facilitate appropriate monitoring for signals of DILI, cases of concurrent AST or ALT and TBL and/or INR elevation, according to the criteria specified above, require the following:

- The event is to be reported to Amgen as a serious adverse event within 24 hours of discovery or notification of the event (i.e., before additional etiologic investigations have been concluded).
- The appropriate electronic Case Report Form (eCRF) that captures information necessary
 to facilitate the evaluation of treatment-emergent liver abnormalities is to be completed
 and sent to Amgen.

Other events of hepatotoxicity and potential DILI are to be reported as serious adverse events if they meet the criteria for a serious adverse event defined in Appendix 1.

Additional Clinical Assessments and Observation

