All subjects in whom investigational product(s) or protocol-required therapies is/are withheld (either permanently or conditionally) due to potential DILI as specified in Table 2 or who experience AST or ALT elevations >3 x upper limit of normal (ULN) or 2-fold increases above baseline values for subjects with elevated values before drug are to undergo a period of "close observation" until abnormalities return to normal or to the subject's baseline levels.

Assessments that are to be performed during this period include:

- Repeat AST, ALT, ALP, bilirubin (total and direct), and INR within 24 hours
- In cases of TBL >2x ULN or INR > 1.5, retesting of liver tests, bilirubin (total and direct) and INR is to be performed every 24 hours until laboratory abnormalities improve.

Testing frequency of the above laboratory tests may decrease if the abnormalities stabilize or the investigational product(s) or protocol-required therapies has/have been discontinued AND the subject is asymptomatic.

Initiate investigation of alternative causes for elevated AST or ALT and/or elevated TBL.

The following are to be considered depending on the clinical situation:

• Complete blood count with differential to assess for eosinophilia

18 May 2022 Page 65 of 69

- Serum total immunoglobulin G, anti-nuclear antibody anti-smooth muscle antibody, and liver kidney microsomal antibody-1 to assess for autoimmune hepatitis
- Serum acetaminophen (paracetamol) levels
- A more detailed history of:
 - o Prior and/or concurrent disease or illness
 - o Exposure to environmental and/or industrial chemical agents
 - O Symptoms (if applicable) including right upper quadrant pain, hypersensitivitytype reactions, fatigue, nausea, vomiting, and fever
 - o Prior and/or concurrent use of alcohol, recreational drugs, and special diets
 - Concomitant use of medications (including nonprescription medicines and herbal and dietary supplements), plants, and mushrooms
- Viral serologies
- Creatine phosphokinase, haptoglobin, lactate dehydrogenase, and peripheral blood smear
- Appropriate liver imaging if clinically indicated
- Appropriate blood sampling for pharmacokinetic analysis, if this has not already been collected
- Hepatology consult (liver biopsy may be considered in consultation with a hepatologist).

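### The permanent-stop liver rule in Appendix 7 omits subjects whose AST/ALT starts at or above ULN, whom exclusion criterion 10 can admit

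*Protocol*

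**What the plan says.** **Permanent stop (Protocol Appendix 7, Table 2).** Three things must hold together: bilirubin above 2x ULN or INR above 1.5x ULN; no important alternative cause; and AST/ALT ">3x ULN (when baseline" was below ULN. The inequality is strict, and no AST/ALT threshold is given for any other baseline.

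**Temporary withholding (same table).** Six conditions, none depending on baseline:
- bilirubin above 3x ULN
- AST/ALT above 8x ULN
- AST/ALT ">5x ULN but $<8x$ ULN for ≥ 2 weeks"
- AST/ALT in that same range in a subject who cannot follow enhanced monitoring
- AST/ALT above 3x ULN with signs or symptoms of hepatitis
- ALP above 8x ULN

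**Eligibility (Section 4.2, criterion 10).** "ALT or AST should be ≤ULN at Screening or Check-in", so a value equal to ULN passes at the first test. After one repeat a subject may still be enrolled if "repeated values above ULN are deemed not clinically significant by the Investigator [eg, 1.5 x ULN". The 1.5x figure is an example, not a cap.

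**Elsewhere in Appendix 7.** The 24-hour serious-event report for liver injury applies to "cases of concurrent AST or ALT and TBL and/or INR elevation, according to the criteria specified above". Close observation starts at AST or ALT above 3x ULN, or at "2-fold increases above baseline values for subjects with elevated values before drug". So the appendix does foresee raised baselines, but only for observation.

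**The concern.** The protocol can knowingly enroll subjects with AST/ALT at or above ULN, but its main rule for combined liver injury does not reach them. Two subjects with identical Day 8 results would be handled differently by Table 2 only because one began at or above ULN.

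Raised liver enzymes are a named sotorasib risk, and the stated mitigation is liver monitoring (Section 1.4.1.2). The decision at stake is whether the Day 9 dose of sotorasib, with omeprazole, goes ahead. The Schedule of Assessments (Appendix 8) has four safety laboratory draws: Screening, Check-in, Day 8 and Day 11. Day 8 is the only one between the two sotorasib doses. The Day 11 draw comes after the last dose, so there the gap could matter only for reporting.

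**Working it through.** No stated figure needs reproducing. The check compares the baselines admitted with the baselines covered, then runs one case through Table 2. All values are multiples of ULN. Appendix 7 does not define baseline. SAP Section 8.1.4 takes the last value before dosing, which on this schedule is normally the Check-in value.

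**1. Coverage by baseline B**

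| B | Admitted by criterion 10? | Permanent-stop AST/ALT limb? |
|---|---|---|
| below 1.0 | yes | yes |
| exactly 1.0 | yes, no repeat needed | no |
| above 1.0 | yes, on repeat, by judgement | no |

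**2. Worked case: Day 8, ALT 4, bilirubin 2.5, ALP not above 8, no symptoms, no alternative cause**

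Withholding conditions:
- bilirubin 2.5 > 3: no
- ALT 4 > 8: no
- 5 < 4 < 8 for two weeks: no
- 5 < 4 < 8 and unable to adhere: no
- ALT > 3 with symptoms: ALT yes, symptoms no, so not met
- ALP > 8: no

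Result: 0 of 6.

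Permanent stop: bilirubin 2.5 > 2, yes; ALT 4 > 3, yes; B < 1.0 is then decisive.
- B = 0.9: yes, so permanent discontinuation
- B = 1.0: no (fold rise 4/1.0 = 4.0)
- B = 1.5: no (fold rise 4/1.5 = 2.7)

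An INR variant (ALT 4, bilirubin 1.5, INR 1.6) gives the same pattern.

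**3. Region that Table 2 leaves uncovered for B ≥ 1.0**

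Assume no symptoms, ALP ≤ 8, no alternative cause, and ability to follow monitoring:
- (a) AST/ALT above 3 and up to 8, with bilirubin above 2 and up to 3
- (b) AST/ALT above 3 and up to 8, with INR above 1.5 and bilirubin up to 3

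At the edge, ALT 8.0 with bilirubin 3.0 meets no withholding row; ALT 8.1 or bilirubin 3.1 does. Inside the 5-to-8 band, the two-week row cannot act in time, because Day 9 − Day 1 = 8 days, which is less than 14. The inability-to-adhere row will not normally apply to a subject confined to the unit.

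**4. Do the two candidate repairs agree?**

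Compare >3 for everyone with >3 and at least 2B. Twice baseline is 2.0, 2.5 and 3.0 at B = 1.0, 1.25 and 1.5, never above 3, so the two give the same decision up to B = 1.5. Above that they differ: 2B = 3.5 at B = 1.75 and 4.0 at B = 2.0.

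**5. Cost if one Day 9 dose is lost**

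The 90% CI half-width on the log scale is proportional to t(0.95, n−1)/√n at a fixed within-subject SD.
- n = 14: 0.4733; n = 13: 0.4943; ratio 1.044
- n = 12: 0.5184; n = 11: 0.5465; ratio 1.054

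**The case against.** The strongest reply is that Table 2 is not the only way to stop dosing, and much of this stands.

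- **Section 4.5.** Any Grade ≥3 adverse event requires withdrawal from dosing, whatever the baseline. A clinically relevant change in compliance with an eligibility criterion that affects safety also requires it, and the worked case departs plainly from criterion 10. The Investigator may also withdraw a subject for clinically relevant signs or symptoms. The documents do not give the CTCAE liver cut-offs, so the share of the uncovered region already caught by the Grade ≥3 rule cannot be sized. These routes are not equivalent to a Table 2 row. Apart from the Grade ≥3 rule they turn on Investigator judgement, and under Appendix 1 a laboratory value becomes an adverse event only if the Investigator considers it clinically significant.
- **INR.** A reader might infer from Appendix 2 ("International normalized ratio will be tested if hepatotoxicity is suspected, per guidelines presented in Appendix 7") that INR could go unmeasured. The documents do not support that. Close observation requires INR within 24 hours for any AST or ALT above 3x ULN, which includes every subject in region (b). Close observation adds tests and a search for causes, but does not itself stop dosing.
- **Rechallenge.** A reader might infer that these subjects could be freely redosed after withholding because they escape the permanent bar. The text is narrower: "Rechallenge may be considered if an alternative cause for impaired liver tests", and the abnormalities must also have resolved. Only one sotorasib dose remains in any case.
- **Status of the appendix.** Its title speaks of suggested actions, and treating raised baselines differently is not an error in itself. Here, though, the different treatment is the absence of any permanent-stop limb, not a limb with another threshold.

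**Conclusion.** The gap is real in Table 2 and minor in consequence. For subjects admitted at or above ULN, an asymptomatic combined elevation in the region above normally meets no stop or withholding row before Day 9, while the same values from a baseline below ULN require permanent discontinuation. The 24-hour DILI reporting trigger arguably inherits the gap, since it refers back to the same criteria; other potential liver injury is still reportable if it meets the Appendix 1 definition of serious.

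A reader might go further and infer that these subjects have no stopping rule at all. The documents do not support that: the withholding rows, the Section 4.5 routes and close observation all apply to them. Nor does the point touch the PK analysis method.

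The number affected is unknown and may be zero of at most 14. Harm needs a baseline at or above ULN, a combined rise after one dose, no symptoms, no alternative cause, and a decision to dose anyway. The conclusion assumes that the baseline qualifier sits in the permanent-discontinuation column, as the legible text shows, and that baseline means the last predose value. The correction should be made because it is short and removes reliance on discretion for subjects the protocol chooses to admit.

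**What to change.** In Table 2, do one of the following:

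1. Change the baseline qualifier to ≤ULN and add, for baselines above ULN, a limb of >3x ULN and at least 2x baseline. The 2-fold rise is already used in Appendix 7, but only to start close observation; using it to stop dosing is new and needs clinical agreement.
2. Delete the qualifier, so that >3x ULN applies to everyone. This is simpler, but would stop a subject with a baseline of 2.0x ULN just above a 1.5-fold rise (3/2.0).

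The options agree for baselines up to 1.5x ULN. Tightening criterion 10 to bar values above ULN is another route, but alone it would still leave a baseline equal to ULN uncovered. Apply the same limb to the 24-hour DILI serious-event report. No other row of Table 2 needs to change.

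The cost is one line of text and no new test. Any Table 2 row already needs the Day 8 result before Day 9 dosing; the protocol states no turnaround, and the change adds no timing demand of its own. A subject may occasionally lose the Day 9 dose and leave the paired analysis, and Section 4.5 says drug-related withdrawals are generally not replaced. Losing one pair costs about 4% (14 to 13 subjects) or 5% (12 to 11) in 90% CI half-width on the log scale.

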Appendix 8: Schedule of Assessments

18 May 2022 Page 67 of 69

	Screening	Check- in	Sotora	sib (Day 1	l) and On Alone	neprazole (Day	y 4-8)		rasib in Comb	oination with
Study Procedures	Days -28 to -2	Day -1	Day 1	Day 2	Day 3	Days 4 to 7	Day 8	Day 9	Day 10	Day 11 (EOS/ET)
Confined to the CRU		X	X	X	X	X	X	X	X	X
Outpatient Visit	X									
Inclusion/Exclusion Criteria	X	X								
Informed Consent	X									
Demographics	X									
Serology	X									
Medical History	X	Xa								
Height and BMI	X									
Weight	X	X								X^b
Drug Screen	X	X								
Alcohol Test		X								
Pregnancy Test (females only) ^c	X	X								X ^b
FSH (postmenopausal females only)	X									
12-lead Electrocardiogram ^d	X	X	X					X		X^b
Vital Signs ^e	X	X	X	X	X			X	X	X^{b}
Clinical Laboratory Evaluations ^f	X	X					X			X^{b}
eGFR ^g	X	X								
Thyroid-stimulating Hormone	X	X								X
Physical Examinationh	X	X								X^b
Sotorasib Dosei			X					X		
Omeprazole Dose ^j						X	X	X		
Sotorasib PK Blood Samples ^k			X	X	X			X	X	X
Adverse Event Monitoring ¹							X			
Serious Adverse Event Monitoring ¹	X					X				
Prior/Concomitant Medications ^m	X					X				

18 May 2022 Page 68 of 69

CONFIDENTIAL AMG 510 20220024

Abbreviations: BMI = body mass index; CRU = Clinical Research Unit; eGFR = estimated glomerular filtration rate; EOS = end of study; AT = early termination; FSH = follicle-stimulating hormone; PK = pharmacokinetic.

- ^a Interim medical history only.
- ^b Assessment to be performed at the EOS or ET.
- ^c Performed in serum at Screening and in urine at all other times. A positive urine pregnancy test will be confirmed with a serum pregnancy test.
- d Electrocardiograms (ECGs) will be collected after the subject has rested in the supine position for at least 5 minutes, and will be obtained prior to the scheduled blood draws. ECGs will be assessed at Screening, Check-in, at predose on Days 1 and 9, and at 0.5, 2, and 4 hours following sotorasib administration; and at EOS or ET. Triplicate ECGs will only be collected at Screening and Check-in if needed to verify eligibility criteria. The 30-minute postdose ECG measurement will have a collection window of \pm 5 minutes, the 2-hour postdose ECG measurement will have a collection window of \pm 10 minutes.
- e Vital signs measurements (oral body temperature, respiratory rate, supine blood pressure, and supine heart rate) will be carried out, prior to having blood drawn, at Screening, Check-in, predose, and at 1, 24, and 48 hours after each dose of sotorasib, and at EOS or ET. Blood pressure and heart rate will be measured using the same arm for each reading after the subject has been resting in the supine position for at least 5 minutes.
- ^fClinical chemistry (fasted at least 8 hours), hematology, and urinalysis.
- g eGFR will be calculated using the Modification of Diet in Renal Disease equation.
- ^h A full physical examination at Screening and Check-in and a symptom-directed physical examination at EOS or ET.
- ¹ Dose administration of sotorasib is to occur during the mornings of Days 1 and 9 following an overnight fast of at least 10 hours. On Day 9, sotorasib administration will occur within 5 minutes after administration of omeprazole with an acidic beverage (Coca-Cola®).
- ^j Dose administration of omeprazole is to occur during the mornings of Days 4 through 9 following an overnight fast of at least 10 hours.
- k Blood samples for determination of sotorasib plasma concentrations and PK parameters will be collected: Predose (Hour 0), 0.5, 1, 1.5, 2, 3, 4, 6, 8, 10, 12, 24, 36, and 48 hours postdose following administration of sotorasib on Days 1 and 9. The PK sample collected 30 minutes postdose will have a sampling window of ± 2 minutes, samples collected from 1 through 3 hours postdose will have a sampling window of ± 5 minutes, samples collected from 4 through 10 hours postdose will have a sampling window of ± 10 minutes, and samples collected from 12 through 48 hours postdose will have a sampling window of ± 20 minutes. Times of all PK samples will be recorded to the nearest minute.
- ¹ Adverse events will be recorded from initiation of study treatment on Day 1 until EOS or ET. Serious adverse events will be recorded from the time the subject signs the Informed Consent Form through 30 days after the last dose of study treatment or until EOS or ET (whichever is later).
- ^m Prior and concomitant medication administration will be recorded from the time the subject signs the Informed Consent Form. In addition, all Investigator-approved medications (prescription or over the counter), all herbal medicines (eg, St. John's wort), vitamins, and supplements taken by a subject within 30 days or 5 half-lives (whichever is longer) prior to enrollment will be recorded on the subject's electronic Case Report Form.

18 May 2022 Page 69 of 69
